Based on the evidence discussed in above, lower MHC-I gene expression, including MHC-I protein expression, in skeletal muscle results in lower content of Type I fibers in skeletal muscle, and as observed in humans with obesity. We propose to understand biological mechanisms that sustain lower MHC-I expression in muscle of humans with obesity by employing experimental tools that are known to stimulate MHC-I gene expression. In non-obese, healthy humans aerobic exercise increases MHC-I, while decreases MHC-IIx, isoform content in skeletal muscle (52, 61), and there is good evidence showing that exercise can reverse dysregulated metabolism seen in muscle of humans with obesity (50, 62). However, other evidence shows that humans with obesity can be “exercise resistant” (63, 64). Our preliminary evidence shows that, although synthesis of MHC-I fails to increase, mRNA of MHC-I increases immediately after aerobic exercise in subjects with obesity. Therefore, acute exercise can be used as an experimental tool to experimentally manipulate mRNA expression of MHC isoforms, and specifically the slow MHC gene/MYH7 mRNA that is responsible for determining the overall muscle fiber phenotype. Failure to increase the synthesis of MHC-I despite increase in MHC-I mRNA expression after exercise in our preliminary studies provides evidence for “translational resistance” with respect of MHC-I expression. These data, therefore, point to reduced rate of MHC-I translation, as cause, at least in part, for reduced MHC-I synthesis, and thus lower content of MHC-I-containing fibers in muscle of humans with obesity. Increasing the plasma amino acid supply to skeletal muscle stimulates acutely the process of overall translation in muscle (65-68), and by enhancing assembly of the active eIF4F complex (69, 70). We have previously shown that increasing the plasma amino acid concentration alone, increases overall protein synthesis in muscle of humans with obesity (8). We propose to couple the response of increased MHC-I mRNA expression after exercise in subjects with obesity to increased plasma amino acids, and which we will employ as a second experimental tool to experimentally upregulate the overall translation process in skeletal muscle. That way we will discover on whether impaired global translation in muscle contributes to the lower synthesis and thus MHC-I expression in muscle of humans with obesity. We expect increased synthesis rate of MHC-I in the presence of increased plasma amino acids after exercise, suggesting that it is impaired global translation in muscle that

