
Date: February 23, 2024

Protocol V11

contributes to lower synthesis and expression of MHC-I. On the other hand, failure to increase synthesis rate of MHC-I under these conditions, will suggest a defect that is specific to the MHC-I translation. Our studies will, therefore, pinpoint specific biological defects that sustain unfavorable muscle fiber phenotype in humans with obesity, and which is key in any effort to address metabolic abnormalities (i.e., impaired muscle glucose uptake) originating from an unfavorable muscle fiber phenotype in these humans.

Specific Aims

Aim 1. To determine the turnover rate of MHC isoforms and overall muscle protein in skeletal muscle of subjects with obesity and lean controls in the basal state. We hypothesize lower synthesis rate of MHC-I (due at least in part to lower MHC-I mRNA) along with lower overall muscle protein synthesis in skeletal muscle of humans with obesity, and concomitant with lower formation of the eukaryotic initiation factor 4F (eIF4F) in muscle (key protein-complex signaling overall translation/synthesis). We hypothesize that muscle MHC-IIx synthesis is not reduced in obesity, and despite lower eIF4F complex formation in muscle, because the presence of higher MHC-IIx mRNA expression in muscle of humans with obesity.

Aim 2. To determine stimulation of the turnover rate of MHC isoforms in skeletal muscle of subjects with obesity and lean controls by plasma amino acids and with and without prior exercise. We hypothesize that increasing the plasma amino acid concentrations alone increases the basal rate of synthesis across all MHC isoforms in both lean and obese subjects, revealing a response largely dependent upon their respective mRNA expressions. This is because plasma amino acids enhance the overall protein translation in muscle (i.e., increase muscle eIF4F complex formation). We hypothesize that acute aerobic exercise alone does not increase the basal-state MHC-I synthesis rate in either lean or obese subjects, and despite greater increase in MHC-I mRNA expression in muscle of subjects with obesity. Thus, we also hypothesize that coupling the plasma amino acid stimulus to the exercise stimulus will increase the synthesis rate of the MHC-I in the subjects with obesity, revealing that impaired overall muscle protein translation is also responsible (and in addition to lower basal-state MHC-I mRNA, Aim#1) for lower MHC-I expression in muscle of humans with obesity.

Approach

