Blood samples will be collected for the determinations of leucine and phenylalanine stable isotope enrichments, as well as plasma chemistry parameters (i.e., glucose, insulin, amino acids, glucagon). Skeletal muscle samples (~150 mg/biopsy) will be analyzed for amino acid enrichment of muscle proteins for the determination of rates of protein turnover (i.e., synthesis, breakdown) of groups of proteins (i.e., mixed-muscle, mixed-mitochondrial protein) as well as individual proteins (i.e., MHC-I, MHC-IIa, MHC-IIx) in the Basal (1st and 2nd biopsies) and Experimental (3rd and 4th biopsies) study periods. Protein turnover measurements related to the experimental manipulations will be performed in the later part of the Experimental period (3rd and 4th biopsies), given that protein synthesis decreases during exercise, but it increases immediately after the cessation of the exercise (94). We will isolate muscle fibers in the collected skeletal muscle samples from either the 1st or 2nd biopsies (i.e., Basal state only) to characterize their MHC isoform content (i.e., MHC-I, MHCII-a, MHC-IIx). We will utilize these muscle fibers to also evaluate the metabolome, transcriptome, and proteome of the muscle fibers to better characterize the overall protein phenotype in skeletal muscle of humans with obesity, and together with the measurements of the turnover rate of the MHC isoforms discussed herein.

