We will study equal number of males and females. We have detected a difference of 1.1 SD with respect to eIF4F complex formation in the Basal state between subjects with obesity and lean controls. Therefore, a sample of 17 subjects with obesity and 17 lean subjects will have sufficient power (80%) to detect 1.1 SD difference ($\alpha = 0.05$) in eIF4F complex formation, and also will have >95% power ($\alpha = 0.05$) to detect a difference of 2.0 SD and 3.5 SD with respect to the rates of mixed-muscle protein synthesis and breakdown, respectively. Also, in the Basal state, we have detected a difference of 2.9 SD for MHC-I synthesis between groups, suggesting that 17 subjects/group will have >95% power to detect this difference ($\alpha = 0.05$). With respect to mRNA responses in the Basal state, we have detected a difference of 1.26 SD for MHC-IIx expression suggesting that a sample of 17 subjects/group will have >80% power to detect significant difference in this variable between groups ($\alpha = 0.05$). We have reported a difference of 2.3 SD in increasing mixed-muscle protein synthesis with increased plasma amino acid concentrations alone in humans with obesity (8). Considering a conservative estimate of a difference of at least half of that (i.e., 1.15 SD) in the response of the MHC-I, 17 subjects/group will provide >90% power ($\alpha = 0.05$) to detect statistically significant increase from Basal in the rate of synthesis of MHC-I in response to the increase in plasma amino acid concentrations coupled to the exercise stimulus in the subjects with obesity ($\alpha = 0.05$). We will test another 17 subjects with obesity that will serve as controls (i.e., increase in plasma amino acid concentrations alone), for a total of 34 subjects with obesity participating in the study. The same experiments will be performed in lean subjects, and where 17 subjects will undergo increase in plasma amino acid

Date: February 23, 2024

Protocol V11

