concentrations coupled to the exercise stimulus, and another 17 will serve as controls, for a total 34 lean subjects participating in the study. Main outcome in the exercise-alone studies is the increase in MHC-I mRNA expression after aerobic exercise, and which we show to increase only in the subjects with obesity. In our preliminary studies we detected a difference of 0.94 SD for MHC-I mRNA expression between before and after exercise in subjects with obesity. A sample of 9 subjects per group will have sufficient power (80%) to detect 0.94 SD difference ($\alpha = 0.05$) in MHC-I mRNA expression. Therefore, we will study 9 lean subjects and 9 subjects with obesity in the groups that will undergo exercise-alone trial. Sample size estimates and power were calculated using paired t-tests with an overall $\alpha = 0.05$ and $\alpha = 0.0125$ for Bonferroni-adjusted multiple comparisons. We propose to enroll 2 more subjects/group for the amino acid infusion and exercise+amino acid infusion studies (to the overall 34 subjects per group indicated above for those studies), to account for unsuccessful experiments and/or increase the statistical power in pair-wise comparisons with the lowest effect size, for a total of 36 lean subjects and 36 subjects with obesity for the studies related to the amino acid infusion and exercise+amino acid infusion. Therefore, we will enroll a total of 90 subjects.

Protection of Human Subjects

Risks to Human Subjects

Human Subjects Involvement, Characteristics, and Design

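### Absence of a rise in MHC-I synthesis after exercise plus amino acids is read as an MHC-I-specific translation defect without using the other-isoform, mRNA and eIF4F responses the plan already measures

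*Combined protocol and SAP*

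**What the plan says.** The end of the Significance section sets out how the exercise-plus-amino-acid (EX+AA) result in subjects with obesity will be read. The expected branch is: "We expect increased synthesis rate of MHC-I in the presence of increased plasma amino acids after exercise". That result would point to impaired global translation. The other branch is: "failure to increase synthesis rate of MHC-I under these conditions, will suggest a defect that is specific to the MHC-I translation". The conditions meant are raised plasma amino acids after exercise. Neither branch mentions another isoform, mixed-muscle protein, mRNA or eIF4F.

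The relevant data are planned:
- 'Variables Determined in Muscle and Blood Samples' provides synthesis rates for mixed-muscle protein "as well as individual proteins (i.e., MHC-I, MHC-IIa, MHC-IIx) in the Basal" and Experimental periods.
- The same section evaluates isoform mRNA and the eIF4G·eIF4E complex in the post-stimulus biopsies.
- 'Statistical Design and Power' lists isoform mRNA and eIF4F formation among the main end-points.
- Aim 2 expects amino acids alone to raise eIF4F formation and the synthesis of all isoforms, to a degree that depends largely on each isoform's mRNA.

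The named analysis is a 2-way repeated measures ANOVA with unstated factors. No isoform contrast, stimulus check or power for the MHC-IIa or MHC-IIx response is given.

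**The concern.** Three situations give the same MHC-I result: a translation defect confined to MHC-I, a weak response common to all isoforms, and a stimulus that did not raise translation initiation or MHC-I mRNA. Only the first is a specific defect, but the inference as written assigns all three to it. It has no branch for a general non-response or a stimulus not achieved.

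It also lets a non-significant rise stand for no rise. Even a well-established absence of an MHC-I response would not show specificity, because that needs a comparison with other proteins in the same subjects. The section goes on to say that the studies will identify specific biological defects, so the mechanistic conclusion leans on this reading.

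**Working it through.** **Inputs from the plan ('Statistical Design and Power').** The MHC-I planning value is half of a mixed-muscle result: "We have reported a difference of 2.3 SD in increasing mixed-muscle protein synthesis with increased plasma amino acid concentrations alone in humans with obesity", then "Considering a conservative estimate of a difference of at least half of that (i.e., 1.15 SD) in the response of the MHC-I". So 2.3 / 2 = 1.15 SD, with n = 17 in the obese EX+AA group. The power claim is "17 subjects/group will provide >90% power" at alpha 0.05. The method is "Sample size estimates and power were calculated using paired t-tests with an overall" alpha of 0.05, and 0.0125 "for Bonferroni-adjusted multiple comparisons". Sidedness is not stated; two-sided is assumed.

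**The plan's own figure.** For a paired t-test the noncentrality is d√n = 1.15 × √17 = 4.74 on 16 degrees of freedom. Exact power is 99.3% at 0.05 and 96.1% at 0.0125. A two-sample version with 17 per arm gives 90.2% at 0.05. At 0.05 the stated figure is met either way.

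**How often the MHC-I-only reading returns 'specific' when nothing is specific.** Assume the same true response d, in SD of the change, in all isoforms. The probability that MHC-I is not significantly increased is P(T ≤ t_crit), with T noncentral t (16 df, noncentrality d√17) and t_crit = 2.120 at 0.05. This does not depend on the correlation between isoforms.

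| True common response | alpha 0.05 | alpha 0.0125 |
|---|---|---|
| 0 SD | 97.5% | 99.4% |
| 0.5 SD | 51% | 74% |
| 0.575 SD (half of 1.15) | 39.5% | 64% |
| 0.75 SD | 17% | 38.5% |
| 1.15 SD (planned) | 0.7% | 3.9% |

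At 0 SD, counting only non-significant results, so that a significant fall is not a failure to rise, gives 95% and 98.75%. With 18 subjects, the number after the enrolment allowance, the 0.5 SD row becomes 48% and 72%.

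**Adding a within-subject contrast.** Let C = mean of the MHC-IIa and MHC-IIx changes minus the MHC-I change. With unit SDs and correlation ρ, Var(C) = (1 + ρ)/2 + 1 − 2ρ = 1.5 − 1.5ρ, so SD(C) = 0.866 at ρ = 0.5. The documents give no isoform SDs or correlations; ρ = 0.3 to 0.7 was tried. Requiring both no significant MHC-I rise and a significant C gives a false 'specific' reading in about 2% of trials at 0 or 0.5 SD (alpha 0.05). If the others rise 1.15 SD and MHC-I not at all, C has at least 99% power at 0.05 and at least 95% at 0.0125 (lowest at ρ = 0.3).

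**Why the contrast cannot stand alone.** Suppose MHC-I and MHC-IIa each respond fully at 1.15 SD and MHC-IIx responds at 1.95 SD (assumed, 0.8 SD more). The mean of C is (1.15 + 1.95)/2 − 1.15 = 0.40 SD, or 0.40 / 0.866 = 0.46 standardised. The bare contrast is then significant in 43% of trials although MHC-I has no defect. Also requiring that MHC-I fail to rise cuts this to under 1% and keeps about 97% power for a real defect.

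**Why separate tests are not enough.** Requiring only that MHC-IIa and MHC-IIx each be significant while MHC-I is not still misreads about 6% to 10% of trials at a uniform 0.5 SD (alpha 0.05).

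**The case against.** The strongest reply is that the plan would expose a failed or general non-response. All isoforms, mixed-muscle synthesis, mRNA and eIF4F are measured after the stimulus. The third biopsy is timed for peak signalling, and a separate obese arm receives amino acids alone. A reader might infer from the quoted sentence that the plan makes no such comparison, or that a general non-response would certainly be reported as specific. The documents do not support either. The measurements exist, several are main end-points, and the sentence says only that the result will suggest a defect. What stands against the plan is that nothing in Significance, Aim 2 or the statistical section makes the specific-defect reading depend on those measurements.

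The second reply is that the large error rates need a response well below plan, while the investigators cite earlier evidence that this amino acid infusion raises mixed-muscle synthesis in obesity. That is fair: at 1.15 SD the risk is under 1% at alpha 0.05. But that evidence is for mixed protein and amino acids alone, and 1.15 SD is half of it rather than an observed MHC-I response to the combined stimulus.

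The third reply is that isoforms may respond unequally without any MHC-I defect, since the plan ties responses to mRNA, expects higher MHC-IIx mRNA in obesity, and uses exercise to target MHC-I mRNA. This is correct, and it rules out a bare contrast as the remedy.

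**Conclusion.** The point holds as a gap in the stated inference, not in the data collection. Followed as written, the reading cannot separate an MHC-I-specific defect from a weak general response or a failed stimulus, whatever the power. The chance of the wrong reading is about 97% with no response, 40% at 0.575 SD, 17% at 0.75 SD and under 1% at the planned 1.15 SD (n = 17, two-sided 0.05). It is higher at 0.0125. These figures assume a common true response and an interpreter who uses MHC-I alone. The contrast figures also assume equal SDs and a correlation of 0.5 where not otherwise stated. They illustrate the risk and do not predict this trial's result. The point deserves a change because the conclusion is mechanistic and the remedy uses planned data.

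**What to change.** Replace the two-branch reading at the end of Significance, and repeat the new rule in 'Statistical Design and Power'. In the obese EX+AA group, conclude an MHC-I-specific translation defect only if all of these hold:

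1. eIF4G·eIF4E association and MHC-I mRNA rise from Basal.
2. MHC-IIa/MHC-IIx synthesis (or mixed-muscle synthesis) rises from Basal.
3. MHC-I synthesis does not rise, reported with its confidence interval.
4. A prespecified within-subject isoform-by-period contrast, on log ratios or percent of Basal, shows a smaller MHC-I response, read alongside each isoform's mRNA change.

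Otherwise report a general non-response, a stimulus not achieved, or an inconclusive result, whichever the data show. State that the contrast is not to be used alone. State also the alpha level for each condition.

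The cost is wording and one contrast; no extra subjects, biopsies or assays are needed. The downside is that a specific-defect conclusion becomes harder to reach. The 97% power quoted above covers conditions 3 and 4 only; conditions 1 and 2 can only lower it, as they can only lower the false-reading rate.

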Inclusion criteria: age, 18-45 years old at the time of enrollment; ability to sign informed consent form; body mass index (BMI), 18.0-26.0 kg/m² (lean subjects), 32.0-50.0 kg/m² (subjects with obesity). Although obesity is defined as BMI > 30 kg/m², our laboratory data over the years show greater decrease as well as more homogenous responses in mixed-muscle protein synthesis in subjects with obesity that have higher BMI values. Therefore, studying subjects with BMI > 32.0 kg/m², *enhances our study design* to test our hypotheses, and given also the inconsistent effects of obesity on metabolism resulting from classifying obesity based on BMI alone (71). We will not study humans with BMI >50 kg/m² to minimize variance in the measured responses in the obese subjects group, as well as for practical considerations related to obtaining muscle biopsies from subjects with extreme obesity (we have previously successfully obtained muscle biopsies from subjects with obesity at the BMI range proposed herein (18)). For subjects with BMI value of more than ~45 kg/m² the ability to obtain muscle biopsy depends largely on body fat pattern/distribution. That is, it is feasible to obtain muscle biopsy from subjects with low fat on thigh (i.e., site of muscle biopsy) and despite a high BMI value. So, subjects with BMI more than ~ 45 kg/m² will be asked to come to our CSIU to first evaluate muscle biopsy feasibility and prior to initiating any screening procedures. As part of the screening procedure we will calculate the Matsuda Insulin Sensitivity Index (ISI) from the plasma glucose and insulin responses to an Oral Glucose Tolerance Test (OGTT) (72). Although, overall, we expect subjects with obesity to be less insulin sensitive, this response can vary greatly within subjects with obesity (73) and lean subjects (74). The Matsuda ISI will be used to control in final analyses of the study data for a possible role of the *biological variable of insulin sensitivity* on affecting muscle protein metabolism (74). *Exclusion criteria:* evidence of diabetes (subjects will be excluded based on hyperglycemia-defined criteria and according to the American Diabetes Association criteria for the diagnosis of diabetes (75) that include fasting plasma glucose > 125 mg/dl, 2-h plasma glucose ≥200 mg/dl during OGTT, or A1C ≥6.5%; however, subjects with A1C 5.7–6.4%, impaired fasting glucose, or impaired glucose tolerance (75), indicative of insulin resistance, will be included, because the focus of the proposed studies is on humans with insulin resistance); presence of acute illness; history of liver disease; uncontrolled metabolic disease, including renal disease; heart disease related to atrial fibrillation, history of syncope, limiting or unstable angina, congestive heart failure or ECG documented abnormalities such as >0.2 mV horizontal or downsloping ST-segment depression, or frequent arrhythmias (>10 premature ventricular contractions/min); low hemoglobin or hematocrit; use of anabolic steroids or corticosteroids (within 3 months); not classified as inactive/sedentary based on the Stanford Brief Activity Survey (76) and accelerometry data (77-79); current participation in a weight-loss regimen; extreme dietary practices (i.e., vegan, vegetarian); smoking (cannot abstain as described below); pregnancy; gastro-intestinal surgery; any medication, intake of supplements, other condition or event considered exclusionary by the PI and the study physicians.

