Our main end-points in the proposed studies are the synthesis rates of mixed-muscle protein, mixed-mitochondrial protein, as well as MHC isoforms, particularly MHC-I, whose synthesis rate we found to be lower in subjects with obesity, in our preliminary studies. These preliminary data also show that MHC-I synthesis rate does not increase in response to our experimental manipulation (i.e., exercise stimulus alone) despite an increase in MHC-I mRNA. Therefore, other main end-points are the expression of mRNA of MHC isoforms as well as the formation of the active eIF4F complex, which has key role in translation initiation in skeletal muscle, and which we found in our preliminary studies to be lower in muscle from humans with obesity. Statistical significance will be calculated using 2-way repeated measures ANOVA.

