Research will be initiated only after obtaining approval from the Institutional Review Board (IRB) at Mayo Clinic. We plan on using a variety of recruitment procedures that include advertisement through flyers and online postings on the Arizona State University and the two Mayo Clinic campuses in Arizona, as well as through our subject registry within the Metabolic Program at Mayo Clinic in Arizona. Recruitment of subjects will also be done using physician referrals of participants in our Weight and Wellness Solution program at Mayo Clinic in Arizona.

A member of the study team will explain all experiment-related procedures and risks thoroughly to each subject. Before informed consent is obtained, subjects will be encouraged to thoroughly read the informed consent form and ask questions regarding the outlined procedures and risks. If a subject agrees to participate as a study volunteer and to sign the informed consent form, signature will be obtained in the presence of the principal investigator/co-investigators, postdoctoral fellow, study coordinator, or a CSIU nurse for witness purposes. The signed consent form will be kept on file in the CSIU or the Metabolic Program within the Mayo Clinic Research unit and a copy will be given to the subject.

Protections Against Risk

General Screening: All subjects will have an assessment of their medical history and will undergo a comprehensive physical exam at the time of enrollment. Subjects will be screened with a routine physical examination, blood tests including cell count and liver function, urinalysis, blood glucose, electrolytes, and electrocardiogram. [name], will examine the screening results and initial to denote approval for enrolling the subject in the study. Records of approval for enrollment will be kept on file in the CSIU or the Metabolic Program.

Study Procedures: All procedures will be performed by appropriately trained and credentialed personnel under the supervision of [name].

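### The basal lean v obese comparison is observational, but the plan states neither age matching nor an age term; prespecify age and sex as covariates

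*Combined protocol and SAP*

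**What the plan says.** Specific Aims, Aim 1, sets the comparison: turnover of MHC isoforms and overall muscle protein "in skeletal muscle of subjects with obesity and lean controls in the basal state".

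Screening and Enrollment of Human Subjects defines the groups by BMI: "18.0-26.0 kg/m² (lean subjects), 32.0-50.0 kg/m² (subjects with obesity"). The age criterion is common to both: "age, 18-45 years old at the time of enrollment". For analytic control the same section names one variable, insulin sensitivity: "The Matsuda ISI will be used to control in final analyses of the study data for a possible role of the" (the sentence then names that variable). It adds that subjects with obesity are expected, overall, to be less insulin sensitive. Activity and extreme diet are handled by exclusion.

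Statistical Design and Power gives the analysis in one sentence: "Statistical significance will be calculated using 2-way repeated measures ANOVA". It does not name the factors and lists no covariates. On sex it says: "We will study equal number of males and females". It does not say whether the balance holds within each BMI group, within each trial arm, or only across the study.

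Recruitment and Informed Consent lists several channels. They include "advertisement through flyers and online postings on the Arizona State University"; similar postings at Mayo Clinic sites; a subject registry; and "physician referrals of participants in our Weight and Wellness Solution program".

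**The concern.** A group factor set by BMI carries with it whatever else differs between lean people and people with obesity who volunteer. Age is an obvious candidate. The window spans 27 years, and a university posting and a clinical weight programme need not reach people of the same age. The protocol accepts that age can matter for these endpoints: under Human Subjects Involvement it leaves out children because growth could confound muscle protein metabolism. Across the adult range it states no further control.

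If the groups differ systematically in age and the endpoint varies with age, the unadjusted contrast mixes the two. Aim 1 would then report an age difference in synthesis rate, mRNA or eIF4F formation as an obesity effect. Adjusting for Matsuda ISI does not stand in for adjusting for age.

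**Working it through.** **Inputs from the plan (Statistical Design and Power).** Basal eIF4F difference 1.1 SD; 17 v 17; alpha 0.05; 80% power. Other basal between-group differences: 1.26 SD (MHC-IIx mRNA), 2.0 (mixed-muscle synthesis), 2.9 (MHC-I synthesis), 3.5 (mixed-muscle breakdown). There are 34 per BMI group when the two amino acid arms are pooled, and 36 enrolled.

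**Assumptions, not in the documents.** Ages spread evenly over 18-45, and a within-group slope of 0.02 to 0.05 outcome SD per year of age. The upper slope implies 0.05 × 27 = 1.35 SD from age 18 to 45, which is steep.

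**1. The plan's own figure.** For a two-sample t-test, the noncentrality is d·√(n/2) = 1.1 × √(17/2) = 3.21 on 32 df. At two-sided 0.05 the power is 87.5%, and 80% needs 15 per group. The stated 80% at 17 is therefore met with some margin. The plan says power came from paired t-tests; lean v obese is unpaired, so the two-sample form is used here.

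**2. Chance age gaps.** Age SD = 27/√12 = 7.8 years. The standard error of the difference in mean age is 7.8 × √(2/n): 2.67 years at 17 per group and 1.89 at 34. The 95% ranges are ±5.2 and ±3.7 years. These are not bias. If both groups come from the same age distribution, the chance imbalance is already in the standard error. Simulating that case with slope 0.05 and 17 per group gives 5.0% false positives.

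**3. Systematic age gap.** Bias = gap × slope. For 6 years:
- 6 × 0.02 = 0.12 SD
- 6 × 0.05 = 0.30 SD

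With no true difference, the two-sided 5% test then rejects (noncentral t, d = bias):

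| Bias | 17 per group | 34 per group |
|---|---|---|
| 0.12 SD | 6% | 8% |
| 0.30 SD | 14% | 23% |

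A 6-year gap is 6/1.89 = 3.2 standard errors at 34 per group, so it would have to come from differential recruitment.

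**4. Against the planned effects.** 0.12 to 0.30 SD is 11% to 27% of 1.1 SD, 4% to 10% of 2.9 SD, and 3% to 9% of 3.5 SD.

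**5. Cost of adjustment at 17 per group, 1.1 SD, two-sided 0.05.** Two covariates leave 30 df. A 6-year gap inflates the variance of the group effect by 1 + (6/2)²/7.8² = 1.15.
- Unadjusted: 87.5%
- Adjusted, covariates balanced and explaining nothing: 87.3%
- Adjusted, 6-year gap, covariates explaining nothing: 82.5%
- Adjusted, balanced, covariates explaining 10% to 20% of variance: 90.5% to 93.4%

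**6. Sex.** 36 per BMI group split evenly over two arms is 18 per arm, which allows 9 men and 9 women. If equal numbers are kept as closely as possible in an odd-sized group, the forced lean v obese gap is at most 1/17 (6 points) or, in the exercise-alone groups, 1/9 (11 points).

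**The case against.** The strongest reply is that no age confounding has been shown. The documents give no ages by group, and no recruitment channel is tied to an age. The postings also cover the Mayo Clinic campuses, a registry is used as well, and current participation in a weight-loss regimen is an exclusion, which limits the weight-programme route. The slopes are assumed and the direction of any bias is unknown. The anticipated effects are large enough that 0.12 to 0.30 SD would not overturn them. All of this stands, and it limits the point to a missing safeguard.

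Four stronger readings are tempting and are not supported:
- The chance gaps of 5.2 and 3.7 years might be taken as confounding. They are not; the test keeps its 5% level (step 2).
- The sex comparison might be called uncontrolled, or equal numbers impossible. The plan commits to equal numbers, enrolment allows 9 and 9 per arm, and an odd group forces a gap of one person. What remains is a wording gap about where the balance applies.
- The ANOVA might be said to contain only group and time. The plan does not name its factors, and elsewhere it commits to controlling for Matsuda ISI.
- The concern might be extended to Aim 2. Powering there rests on within-subject change from Basal, from which the main effects of age and sex cancel.

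The reply does not remove the need for a rule. The preliminary effect sizes may not recur, and Aim 1 also predicts that MHC-IIx synthesis is not reduced. For a predicted null, a bias of a few tenths of an SD in either direction could mislead.

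**Conclusion.** The point holds for age in the basal lean v obese comparison. The contrast is observational, the age window is common but wide, and the plan states neither matching nor adjustment for age. Under the assumed slopes, a 6-year systematic gap would shift the contrast by 0.12 to 0.30 SD. That is secondary beside 1.1 to 3.5 SD, but material for smaller differences and for the MHC-IIx prediction. A reader might infer that the Aim 1 result is confounded or that its false-positive rate is inflated. The documents support only that it is unprotected, since both the gap and the slope are assumptions. Sex is a minor matter if the equal-numbers plan holds within each BMI group and arm; if it holds only study-wide, the imbalance is not bounded.

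**What to change.** In Statistical Design and Power:
1. Prespecify age (continuous) and sex as covariates in the basal lean v obese comparisons, by ANCOVA or a mixed model, and report the unadjusted result beside the adjusted one.
2. State that equal numbers of males and females apply within each BMI group and each trial arm, as nearly as odd numbers allow.
3. If lean v obese differences in response are also to be adjusted, add age-by-period and sex-by-period terms, or model the change score with these covariates. Age and sex as main effects alone adjust the basal and overall group contrast but leave the within-subject change and a balanced group-by-period test unchanged.

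The cost is a few sentences and two degrees of freedom in the basal model, plus a modest loss of power if the groups do differ in age (step 5). No new data should be needed: age is required for eligibility and sex for the equal-numbers plan.
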